- Unstable heart disease, including hospitalization for any cardiac or vascular event in the past 6 months.
- eGFR <30 ml/min/1.73m2 or hemoglobin <11.0 g/dL measured in the past year
- Cancer that has been under treatment in the past 6 months, or treatment is likely in the 3 months after signing the consent, not including skin cancer or cancers under long-term hormonal reduction treatment (breast or prostate, no other active treatment)
- Psychiatric condition that interferes with daily activities or diabetes self-care, including substance abuse
- Any illness or condition that may interfere with study measurements, or contraindications for use of SGLT2i, based on investigator discretion (hemoglobinopathy, orthostatic hypotension)
- Unwilling to avoid alcohol during the active study periods, specifically to avoid alcohol for 4 hours prior to any breath ketone measurement

- Currently following or planning to adopt a diet that is low in carbohydrates (defined as <90 grams of carbohydrate per day) or is expected to be ketogenic
- Use of oral or injected corticosteroids within the past 30 days or planned during the study period
- Taking disulfiram (due to interference with breath ketone measurements)
- History of vomiting episodes for any reason in the past 30 days, or hospitalization for cyclic vomiting in the past year
- History of urinary tract infection in the past 3 months
- Pregnancy, breast-feeding or intention of becoming pregnant during the study time period and up to 30 days after study completion
- Pre-menopausal women not using acceptable birth control defined as abstinence, surgical sterilization, hysterectomy, hormonal contraception, IUD or proven effective barrier methods

The five study data-collection periods are as follows:

- 1. Visit 1 will collect demographic, medical history, insulin administration and insulin dose data; CGM download, lab draw if needed, and training on capillary ketone measurements using the Precision Xtra meter and breath acetone using the Biosense breath ketone analyzer. Dapagliflozin tablets will be provided to participants randomized to Group B. Recommendations for change in insulin regimen or insulin doses will be made at this visit.

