CGIVI check for connectivity to clinic		X							
supplies breath ketene analyzer		х							
Training on the capillany kotone motor		v							+
Training on the breath ketone analyzer		^							
ensure and download and connectivity		Х							
Training on the study requirements diany		x							
Randomization		X							
CGM download	х	~	х			х			x
Ketone testing 3X daily, capillary and breath	~		~		х	~~~~~~~~~~~~~~~~~~~~~~~~~~~~~~~~~~~~~~~		x	
					~			~	
Home Pregnancy test WOCBP a					x a				
Vital signs of hours and prn					~	х			x
Urine Pregnancy test as needed		х	х			X			X
HbA1c		X							
BMP and CBC b		xb							
CPC PMP POHP AcAc c baseline		Λ				x			×
RMP a 2 hours						×			×
						^ V			×
Laboratory BOHB , ACAC q 1-2 hours						^ V			^ 
Future research stored blood samples						X			X
Capillary BOHB q 1 hour						X			X
Capillary glucose q 1 nour						X			X
Breath ketone measurement q 1 nour						X			X
Standard moal at the end						X			×
						^			
Physician oversight, MDI user if basal insulin adjustment required		x							
Physician oversight, safety assessment		1							
correction insulin dose +/- fluids administered						X			X
Dispense SGLT2i tablets		х							
Adverse events and concomitant medication									
review		х	Х			Х			X
Return and count SGLT2i tablets		1				Х			
Ketone Use Survey f					Х				х
a. Home pregnancy test for WOCBP before start	ting SGLT	2i if 4 we	eks or more	since on-si	te visit 1	ı			-
b. If lab results within 12 months prior to screer	ning are i	not availa	ble						
c. May be performed									
d. May be Gap between Visit 2 and start of SGLT2i segment of up to 2-3 weeks if scheduling issues arise. Subject should NOT start dapagliflozin sooner than 14									
days before Visit 2. Subject must have taken dapagliflozin for 14 consecutive days prior to the day of Visit 2.									
e. May be Gap between Visit 2 & usual care of u	ip to 2-3	weeks							
f. Survey may be provided on paper or electron	ically								

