After the investigator or sub-investigator determines that the participant meets all of the inclusion and none of the exclusion criteria, the study team will proceed with interrogation of the participant's CGM to ensure appropriate connectivity with the study team. Participants will be asked to demonstrate competency in making changes to insulin pump settings. The study team members will train the participant in the use of the Precision Xtra ketone meter and the Biosense BKA. Participants will be instructed to wait 60 minutes after eating, smoking/vaping, drinking sodas or flavored waters or consuming items such as toothpaste, mouthwash, cough drops, breath mints, chewing gum, lip balm and artificial sweeteners before doing a BrACE measurement. If using alcohol, participants should wait 4 hours before testing with the BKA. Participants will be instructed in avoidance of environmental contaminants also. Participants will be able to test capillary BOHB even when conditions are not optimal for BrACE.

The participant will upload the Biosense app onto his or her smart phone and test a test run will be conducted. A diary will be provided for entry of BOHB ketone measurements and BrAce with space for comments in case of known interference with BrAce or other problems with measurements. A written ketone action plan will be provided to all participants in the study. Participants will be informed that they may stop participating in the study at any time without loss of usual care of their diabetes.

A ketone action plan will be provided to each participant that will include the following elements: ingestion of carbohydrates, fluid intake and insulin administration with doses of insulin adjusted according to individual requirements. Participants will be asked to employ the ketone action plan if BOHB reading is >1.5 mmol/L. BrACE levels of >15 in the absence of corresponding BOHB level >1.5 mmol will be considered due to contamination and the participant will be asked to repeat the levels in 1 - 2 hours.

Patients will be randomized by card draw in lots of 4 to Group A or Group B

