At the end of this visit, the next part of the study will be scheduled. The participant will be provided with dapagliflozin, 10 mg, 14 tablets. The participant will be asked to take the pills daily for 14 days prior to Visit 3 which is conducted on-site. If a gap in scheduling occurs such that visits 2 and 3 are more than 4 weeks apart, women of child-bearing potential will be asked to complete a home pregnancy test, with photographic proof that it is negative before starting dapagliflozin.

The ketone action plan will be discussed again with each participant. Elements of the plan will during PERIOD 2 will include: stopping the SGLT2i medication, ingestion of carbohydrates, fluid intake and insulin administration with doses of insulin adjusted according to individual requirements. Participants will be asked to employ the ketone action plan if BOHB reading is >1.5 mmol/L. BrACE levels of >15 in the absence of corresponding BOHB level >1.5 mmol will be considered due to contamination and the participant will be asked to repeat the levels in 1 - 2 hours. Participants will be given numbers of study personnel to call for ongoing advice about management of ketosis.

**USUAL CARE + SGLT2i (**Group B will do this segment first, followed by usual care without SGLT2i) The participant will commence taking dapagliflozin, 10 mg daily, for 14 days before Visit 3. Insulin doses will be reduced by 10% basal and 15% bolus. Insulin dose adjustments will be determined by an investigator at the end of Visit 2. Participants will check BrACE with the Biosense BKA and capillary BOHB with the Precision Xtra ketone test strips when fasting and at two other times during the day. Each time point should be at least 4 hours after ingesting alcohol. Participants will be instructed in avoidance of contamination with other alcohol sources such as swabs, nail polish remover, hand sanitizer and other

solvents during the testing period. The study team will remotely monitor the participant's glucose within a few days of starting the SGLT2i and again prior to the on-site visit to ensure safety. There is no mandated contact with the participant, but participants can contact the study team at any time for questions.

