#### Assessment of Safety

Safety parameters will be analyzed separately for the usual care segments and for the insulin withdrawal days. For the usual care segment, the main safety concern is a level of capillary blood BOHB >1.5 mmol/L at any time. Participants will be asked to call the study coordinator or investigator for advice if this happens, and to start a ketone action plan. The participant can call for concerns about any level of capillary BOHB during the study, but in particular while taking an SGLT2i. The participant will be

provided with a ketone-action plan that will include ingestion of carbohydrates, fluid and insulin administration and frequent follow-up testing. The study investigator will monitor the participant with contact every 1 - 2 hours until the episode resolves. Any capillary blood BOHB level >1.5 mmol/L will be reported as an event of special interest, with follow-up ketone action plan results noted. BrACE levels of >15 without corresponding BOHB level >1.0 mmol/L will be considered likely due to contamination and repeated in 1 hour. Likewise, any severe hypoglycemia event will be reported as an adverse event. Patients with level 2 hypoglycemia, glucoses <54 mg/dL for more then 1% of the day on weekly CGM reviews will have insulin doses adjusted and a discussion with the investigator.

The most important safety parameter of the insulin withdrawal test days will be capillary blood BOHB levels >3 mmol/L, or symptoms of nausea or vomiting at any level of BOHB. Capillary BOHB level of >3 mmol/L constitutes a stopping point for the insulin withdrawal study, and immediate treatment with fluids, insulin and carbohydrates will be commenced, and the patient followed on-site until the episode resolves. Resolution will be defined as cessation of symptoms and capillary BOHB level <1.0 mmol/L, with blood glucose <250 mg/dL. Note that in a similar study of insulin withdrawal before and after treatment with the SGLT2i, canagliflozin, it took about 6 hours for glucose to increase from 100 to 300 mg/dl (pre-treatment) and from 100 to 220 mg/dL with canagliflozin. During the six hours, BOHB increased from 0.2 to 1.2 mmol/L (pre-treatment) and from 0.4 to 1.5 mmol/L with canagliflozin. This proposal uses a similar time sequence, and thus we anticipate similar results from the insulin withdrawal.

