# Ethical considerations

This study will be submitted to the Washington University Human Research Protection Office (HRPO), which is the institutional review board for ethics review and approval. The informed consent will carefully detail the previously described risks to persons with T1D taking a SGLT2i. The risks of insulin withdrawal including hyperglycemia and the development of mild ketosis will be described, along with the stopping rules and treatment plans for resolution of the event. A written informed consent, approved by the WU HRPO, will be used in the study, and consent obtained prior to any study procedure being performed. Ethics concerns for this study include:

- Loss of confidentiality is a risk with this clinical study. This risk will be handled by careful attention to HIPAA guidelines and de-identification of data. All research personnel have been trained in confidentiality measures and good clinical practice.
- Loss of time while performing study-related procedures, both over 4 weeks of ketone monitoring while at home, and on-site study visits. There is no mitigation strategy for this risk, but communication about time commitments and scheduling concerns will be handled both verbally and in writing in the informed consent.
- Hyperglycemia and development of ketones will occur during on-site study visit days due to insulin withdrawal. This could result in symptoms of feeling unwell, nausea or vomiting. This is a clearly identifiable risk. Stopping rules and mitigation strategies of frequent monitoring and treatment to the point of recovery from the event will be described. An investigator will either be present at the end of the visit or be in close proximity for consultation.
- Adverse effects of dapagliflozin will be described. Mitigation strategies will be offered (such as treatment of genital infections), and stopping the drug will be an option.
- Hyperglycemia from insulin dose reduction while starting dapagliflozin or hypoglycemia due to insufficient insulin dose reduction can occur. Both of these risks will be explained at the beginning of the study and at the start of the SGLT2i treatment. Mitigation strategies include daily assessment of glucoses by CGM and insulin dose adjustments to accommodate the added anti-hyperglylcemic treatment.

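### Group B takes dapagliflozin at home under a Visit 1 ketone action plan that does not list stopping the drug

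*Combined protocol and SAP*

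**What the plan says.** The protocol describes the ketone action plan in three places.

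- **VISIT 1.** Every participant receives a plan, used when BOHB exceeds 1.5 mmol/L. Its elements are "ingestion of carbohydrates, fluid intake and insulin administration with doses of insulin adjusted according to individual requirements". There is no separate version for Group B.
- **On-site Visit, closing text.** The plan is gone over again: "Elements of the plan will during PERIOD 2 will include: stopping the SGLT2i medication", followed by the same carbohydrate, fluid and insulin elements. The same text supplies 14 dapagliflozin tablets to be taken before Visit 3.
- **Assessment of Safety.** For the home segments, participants have a "ketone-action plan that will include ingestion of carbohydrates, fluid and insulin administration and frequent follow-up testing".

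On timing, the list of data-collection periods under Research Design says of Visit 1: "Dapagliflozin tablets will be provided to participants randomized to Group B". Footnote d of the Group B schedule adds: "Subject must have taken dapagliflozin for 14 consecutive days prior to the day of Visit 2". That schedule has the tablets returned and counted at Visit 2.

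Outside the action plan, Ethical considerations says of dapagliflozin's adverse effects that "stopping the drug will be an option".

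**The concern.** Ketosis on the drug is the main hazard the trial anticipates. The Rationale reports that DKA on SGLT2 inhibitors ran at 2 to 3 times the placebo incidence even where ketone action plans were in place, and calls DKA potentially life-threatening. During the drug segment insulin is also cut, by 10% basal and 15% bolus. Where the protocol writes a plan for that segment, withdrawing the drug is the first element it lists.

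Group B goes through the same exposure first, yet the plan it holds at that time lacks the step. Footnote d also tells these participants to take the drug on 14 consecutive days before Visit 2, so without a stop instruction the written direction is to continue. At stake is whether both randomized groups have the same on-drug safety instruction. No endpoint or analysis depends on it.

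**Working it through.** No plan figure needs reproducing; this is a check of text and sequence, plus one exposure count.

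**Step 1. Compare the three plan descriptions with Group B's timeline.**

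| Description | When it applies | Lists stopping the drug? | Group B's position |
|---|---|---|---|
| VISIT 1 | Visit 1 onward, everyone | No | About to start dapagliflozin |
| On-site Visit, closing text | End of an insulin-withdrawal visit, for an undefined PERIOD 2 | Yes | Drug segment finished |
| Assessment of Safety | Both home segments | No | On drug in Segment 1, off drug in Segment 2 |

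One of three contains the step, and it comes after Group B's drug segment.

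**Step 2. Test other readings of the middle row.** If the visit meant is Visit 2, Group B has just completed the drug. If it is the usual-care insulin-withdrawal visit, that is Visit 3 for Group B, the end of study. If PERIOD 2 means Segment 2, Group B is in usual care without the drug. If PERIOD 2 loosely means the SGLT2i segment, the step belongs to Group B's Segment 1, but the discussion that conveys it still takes place afterwards and nothing at Visit 1 carries it.

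**Step 3. Look for the same carry-over elsewhere.** Footnote d of the Group B schedule opens "May be Gap between Visit 2 and start of SGLT2i segment of up to 2-3 weeks if scheduling issues arise", although its column lies between Visit 1 and the drug segment and its last sentence requires dosing before Visit 2. The USUAL CARE + SGLT2i text says "Insulin dose adjustments will be determined by an investigator at the end of Visit 2", which for Group B is after the drug. For insulin this is only inconsistent wording, because Research Design already provides dose recommendations at Visit 1.

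**Step 4. Count the exposure.** The inputs are 20 participants, randomization in lots of 4, and 14 days on drug. I assume each lot splits 2:2, which the protocol does not state.

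- Group B: 20 / 4 = 5 lots; 5 × 2 = 10 participants
- Group B on-drug home days: 10 × 14 = 140
- All on-drug home days: 20 × 14 = 280
- Share under the Visit 1 plan: 140 / 280 = 50%

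The omission matters only on days when BOHB exceeds 1.5 mmol/L. The documents give no expected home rate of that, so the count cannot be turned into events.

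**The case against.** The strongest reply is that the procedures are organized by segment and narrated in Group A's order, with headings telling the reader that Group B does the SGLT2i segment first. Taken literally, the closing text would also give Group B its tablets at Visit 2, which the schedule contradicts. Sensible staff would therefore move the stop step along with the drug. That makes correct conduct likely, but it leaves the Visit 1 plan, issued to everyone with its elements spelled out, without the step.

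Second, the written handout is not in the documents, and the protocol's lists may be summaries; the safety section adds follow-up testing that the other two omit. This stands as a limit. The finding concerns the protocol text, and the handout could already be right.

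Third, other safeguards exist. At BOHB above 1.5 mmol/L the participant is asked to call, and an investigator then makes contact every 1 to 2 hours until resolution. Dosing is once daily, so that contact would usually come before the next tablet. This reduces the likely harm, but it depends on the participant making the call. The drug segment has no mandated contact, its remote monitoring is of glucose, and the protocol itself recognizes DKA at lower-than-expected glucose. The statement that participants receive telephone numbers for advice on ketosis also sits in the Group A-ordered text. The option to stop in Ethical considerations is not tied to any ketone level.

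Finally, being first in one list does not prove that stopping has priority, and the 50% restates that half the participants are in Group B. Both points are fair. The finding needs only that the protocol intends the step for people on the drug.

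**Conclusion.** The concern holds. Group B's entire drug segment, about 10 participants and 140 of 280 on-drug home days under 2:2 allocation, runs under an action plan that, as the protocol describes it, lacks a step intended for participants on the drug. The call-in rule, the investigator follow-up and the general option to stop reduce the gap without closing it. The likely harm cannot be quantified from the documents, and the handout may already contain the step. This should be corrected for safety and for consistency between the groups. The visit-number slips taken alone would be clerical.

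**What to change.** - **VISIT 1 plan:** add stopping dapagliflozin for Group B.
- **Assessment of Safety plan:** add stopping dapagliflozin for any participant taking it.
- **On-site Visit closing text and USUAL CARE + SGLT2i:** replace PERIOD 2 with the SGLT2i segment. Replace the end of Visit 2 with the visit at which dapagliflozin is dispensed (Visit 1 for Group B, Visit 2 for Group A). Where drug days are counted to Visit 3, refer to the SGLT2i insulin-withdrawal visit.
- **Group B schedule, footnote d:** place the gap between Visit 1 and the start of the SGLT2i segment.
- **Group B handout:** confirm that it contains the stop step, and revise it if not.

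The cost is protocol wording and possibly a revised handout. No visits, tests or participants are added.

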#### On-site visit, SGLT2i

The on-site visit with SGLT2i will be conducted at the Intensive Research Unit at Washington University, the same format as described for usual care. Patients will be asked to arrive fasting, to stop their basal insulin delivery 1 hour before arrival at the center if on an insulin pump or to hold injectable insulin doses. Prior to leaving home, the participant's blood glucose should be 90 – 250 mg/dL, and BOHB <1.5 mmol/L, or the test day will be rescheduled. Time of the last insulin dose will be recorded. Patients will be given a dose of dapagliflozin, 10 mg upon arrival at the IRU. Vital signs and baseline labs including a CBC, BMP and pregnancy test in women with child-bearing potential will be done. Measurements of capillary BOHB using the Precision Xtra meter and breath ketones using the Biosense BKA will be done hourly X7 if the patient remains relatively asymptomatic, and the capillary BOHB level does not exceed 4 mmol/L. If the capillary BOHB reaches 2.5 mmol/L or capillary glucose reaches 250 mg/dL, the capillary finger sticks and breath measurements may be collected at 30 minute intervals. The venous blood samples will continue to be collected on the hour intervals. Venous blood samples for BMP, BOHB and AcAc\* will be drawn at baseline and every 2 hours X3 plus the end of the study.

The insulin withdrawal portion of the study will end (stopping rules) upon patient request for any reason, if the patient becomes symptomatic with nausea or vomiting (even if he or she does not request that the study be stopped), after 7 hours of fasting without insulin, or if either the capillary BOHB is  $\geq$ 4 mmol/L or the CGM blood glucose is  $\geq$ 400 mg/dL. BMP will be done every 2 hours and at the end of the study. At the termination of the ketogenic fast, participants will be given a correction bolus dose of insulin by IV or subcutaneous injection, restart insulin via insulin pump, and or administer an injection of pre-meal insulin and be given a standard meal. Participants will be observed for 1 hour or more if needed after the study end for reduction in ketones and glucose into safe ranges. Glucose and ketone monitoring will continue into the evening with a phone call or other contact made with the patient for safety.

\*Acetoacetate (AcAc) has been rarely measured in studies of ketone metabolism due to lack of a reliable assay, stability of the analyte and high cost. A plate-based nonenzymatic spectrophotometric assay is now available, but it is new to the WU Core Laboratory. There are several unknowns about the assay. Given the wide range of AcAc levels during ketogenesis, dilution of specimens is recommended, however, the number and extent of dilution is unclear. Therefore, we will plan to draw and store samples for AcAc every 2 hours for a total of 4-5 samples during each of the insulin withdrawal visits. Samples will be batched and run after 4 patients have insulin withdrawal visits, providing 16-20 samples. Once we better understand the assay, the number of dilutions, the stability of the samples and the approximate correlation with BOHB and acetone, we will develop further plans for measurement of AcAc, whether on all participants or a sub-group of participants. Measuring AcAc is of significant interest, but it will be considered an exploratory aim of the study due to technical uncertainties and cost of the assay. This will be reflected in the informed consent.

